5.2.2.11 Time to first respiratory-related hospitalization over the whole trial

Time to first respiratory-related hospitalization assessment will be based on the date of hospitalization collected on a specific hospitalization eCRF page.

For those patients who experience a respiratory-related hospitalization, time to first respiratory-related hospitalization [days] will be computed as:

- Date of first respiratory-related hospitalization – date of first drug intake + 1

Patients who did not experience any event during their trial participation will be censored according to the mechanism for censoring as described in [Table 5.2.2.11: 1](#).

Table 5.2.2.11: 1 Censoring Rules for Time to first respiratory-related hospitalization over the whole trial

Rule #	Situation	Outcome (event or censored)	Date of event or censoring
1	Patient had a documented respiratory-related hospitalization and the date of the event is known	Event	Date of event
2	Patient had a documented respiratory-related hospitalization and the date of the event is unknown	Event	Imputed date of event (imputation see Section 6.6.2.2)
3	Patient did not have a documented respiratory-related hospitalization (no matter whether the patient is alive or died or patient status is unknown)	Censored	Date of last contact when the patient was known to be alive and event free

5.2.2.12 Time to first acute Interstitial Lung Disease (ILD) exacerbation or death over the whole trial

For those patients who either experience acute ILD exacerbations or who die due to any cause at any point in the study, time to first acute ILD exacerbation or death [days] will be computed as:

- Date of first documented acute ILD exacerbation or death (whichever occurs earlier) – date of first drug intake + 1

Patients who did not experience any event during their trial participation will be censored according to the mechanism for censoring as described in [Table 5.2.2.12: 1](#).

Table 5.2.2.12: 1 Censoring Rules for Time to first acute ILD exacerbation or death over the whole trial

Rule #	Situation	Outcome (event or censored)	Date of event or censoring
1	Patient had a documented acute ILD exacerbation or died and the date of the event is known	Event	Earliest Date of event

Table 5.2.2.12: 1 Censoring Rules for Time to first acute ILD exacerbation or death over the whole trial (continued)

Rule #	Situation	Outcome (event or censored)	Date of event or censoring
2	Patient had a documented acute ILD exacerbation or died and the date of the event is unknown	Event	Imputed date of event (imputation see Section 6.6.2.2)
3	Patient did not have a documented acute ILD exacerbation and is alive	Censored	Date of last contact when the patient was known to be alive and event free
4	Patient status is unknown	Censored	Date of last contact when the patient was known to be alive and event free

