| | 
 • N (%) of patients with treatment-emergent pathological findings of epiphyseal growth plate on imaging at week 24, and week 52*; • N (%) of patients with treatment-emergent pathological findings on dental examination or imaging at week 24, and week 52*; • N (%) of patients with treatment-emergent adverse events over the whole trial; • Change in height, sitting height, leg length from baseline at week 24, week 52*, week 76*, and week 100*. • Change in Forced Vital Capacity (FVC) % predicted from baseline at week 24, and week 52*; • Absolute change from baseline in Pediatric Quality of Life Questionnaire™ (PedsQL™) at week 24, and week 52*; • Change in oxygen saturation (SpO₂) on room air at rest from baseline at week 24, and week 52*. • Change in 6-min walk distance from baseline at week 24, and week 52*; • Patient acceptability based on the size of capsules at week 24; • Patient acceptability based on the number of capsules at week 24; • Time to first respiratory-related hospitalization over the whole trial; • Time to first acute Interstitial Lung Disease (ILD) exacerbation or death over the whole trial; • Time to death over the whole trial; 
*52 weeks, 76 weeks, 100 weeks time points will not be available for all patients.
 |
| Trial design | Double blind, randomised, placebo-controlled on top of standard of care (SOC) over 24 weeks, followed by open label active treatment of variable duration. |
| Total number of patients randomised | At least 30 randomised patients including at least 20 adolescents aged 12-17 years. |
| Number of patients on each treatment | Nintedanib: approx. 20* Placebo: approx. 10* *Patients will be allocated to the treatments in a ratio of 2:1 (Nintedanib:Placebo). |
| Diagnosis | Clinically significant fibrosing Interstitial Lung Disease |
| Main in- and exclusion criteria | Main inclusion criteria: Male or female 6 to 17 years old at Visit 2, with evidence of fibrosing ILD on HRCT within 12 months of Visit 1, FVC % predicted $\geq 25\%$ at Visit 2 and clinically significant disease at Visit 2 based on either clinical markers of disease severity or evidence of clinical progression over time. |

| | |
|-------------------------------|--|

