While there is overlap between clinical diagnoses associated with lung fibrosis in paediatrics and adults, some diagnoses associated with lung fibrosis are specific to each population. The following paediatric conditions can be most frequently associated with lung fibrosis in paediatrics:

- surfactant protein deficiency (SFTPC and ABCA3 mutations [i.e. recessive disorder, suspected pathogenic variants or deletion/disruption]);
- chronic hypersensitivity pneumonitis (cHP);
- toxic/radiation and drug induced pneumonitis;
- post haematopoietic stem cell transplant (HSCT) fibrosis;
- connective tissue disease related disorders (e.g. juvenile rheumatoid arthritis [RA]/juvenile idiopathic arthritis, SSc, dermatomyositis/polymyositis [DM/PM]; mixed connective tissue disease [MCTD])
- sarcoidosis.

In addition to difference in clinical diagnoses associated with fibrosing lung disease, the clinical course of fibrotic lung disease also differs between paediatrics and adults.

The data on the natural history of chronic fibrosing interstitial lung disease in children is limited. The available evidence suggests overall that the clinical course is associated with better outcome compared to adult ILDs with survival at 2, 4 and 5 years after symptom onset reported to be 83%, 72% and 64%, respectively [[R09-5337](#)]. This is compared to a median survival of 2.5–3.5 years from diagnosis in IPF [[P11-07084](#)], the most progressive form of fibrosing lung disease in adults. However, as previously mentioned there is a subgroup of children with fibrosing lung disease who experience significant morbidity and mortality [[R09-5337](#)].

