Moreover, the overall exposure to active treatment based on the proposed study design allows for collection of long term safety monitoring data of potential paediatric specific AEs (i.e. bone and teeth effects), which may take longer to develop. Based on to the current design, assuming a recruitment time of 18 months, the treatment period for the minimum targeted 30 subjects is expected to be minimum 26 weeks, with an average nintedanib exposure of approximately 12 months, and >2-year exposure in early enrolled patients. As such, data collected beyond 6 months will provide longer term safety and efficacy information.

Sample Size

The target sample size of a minimum of 30 patients is based on the sample size estimation for the primary evaluation of PK and feasibility. Although the planned basket approach makes it feasible to evaluate this extremely rare patient population, one of the limitations of this approach is the heterogeneity of the study populations, especially in evaluating efficacy outcomes of potential interest (e.g. lung function). Given the high unmet medical need, lack of therapeutic option and the potential for more robust assessment of efficacy, study enrolment into the treatment phase will remain open until 30 patients (at least 20 adolescents

aged 12-17 years, and if feasible at least 10 children aged 6-11 years) have completed PK sampling at 26 weeks, or prematurely discontinued the trial. This approach will allow for any eligible patients identified beyond the minimum targeted 30 subjects to have access to study drug. All PK and clinical data available at DBL 1 (or updated DBL 1) will be used in the primary analysis to allow for more robust estimates of exposure and potential treatment effect.

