6.6.2.2 Time-to-event endpoints

In the analyses of the time-to-event endpoints, missing or incomplete data will be managed by standard survival analysis techniques (i.e. censoring). If a patient has no event then he will be censored as described in [Section 5.2.2](#).

A missing or incomplete date of death will be imputed/completed that the derived date is the earliest possible date which is on or after date of onset of the fatal AE, and on or after treatment start (in case this AE is treatment-emergent), and on or after derived date of last contact.

For the time to first respiratory-related hospitalization, or time to first acute ILD exacerbation, in case of partially missing dates, the following imputation will be done:

- If day is missing, then imputed day will be the 15th of the month
- If day and month are missing, then imputed date will be the 1st of July of the (non-missing) year
- If year is missing, date will not be imputed

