7.5.2.2 Time-to-event endpoints

[figure not shown]
Separate Kaplan-Meier plots will be presented by randomised treatment group and overall (total group) for time-to-event endpoints defined in [Section 5.2.2](#). Kaplan Meier estimates and confidence intervals (using Greenwood variance formula) for the cumulated time-to-event rate will be calculated at 24 weeks and at 52 weeks. Q1, median and Q3 of the time to event will be presented, if reached. No statistical test will be performed.

[figure not shown]

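### Censoring deaths in time to first respiratory hospitalisation makes the Kaplan-Meier rate overstate the proportion hospitalised if any child dies first; add a cumulative incidence with death as a competing event.

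*SAP*

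**What the plan says.** SAP Table 5.2.2.11: 1, rule 3, treats a child without a documented respiratory hospitalisation as censored "no matter whether the patient is alive or died or patient status is unknown". The censoring date begins "Date of last contact when the patient was known to be alive" and adds that the child must also be event free, so a child who dies leaves the risk set at or shortly before death.

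SAP 7.5.2.2 sets the estimator: "Separate Kaplan-Meier plots will be presented by randomised treatment group and overall (total group) for time-to-event endpoints". Estimates with Greenwood confidence intervals "for the cumulated time-to-event rate will be calculated at 24 weeks and at 52 weeks", and Q1, median and Q3 of the time to event are shown if reached. No test is planned. SAP 6.6.2.2 names only censoring as the technique for these endpoints. Protocol 7.2.3 and the synopsis also specify Kaplan-Meier for time-to-event endpoints.

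The visible text names no competing-risk method and does not say that a rate in the absence of death is the target. Death is captured elsewhere: it is an event in the exacerbation-or-death endpoint (SAP 5.2.2.12), and time to death is a separate endpoint (SAP 5.2.2.13).

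**The concern.** A child who has died cannot be hospitalised later. Kaplan-Meier handles a censored child as someone who could still have the event and spreads that child's weight over those still followed. When the censoring is a death, this adds probability of hospitalisation that can never be realised. The figure is labelled a cumulated event rate and will naturally be read as the proportion of children hospitalised by that week, which it then exceeds.

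Deaths cannot be assumed absent. Protocol 1.3.1 cites "survival at 2, 4 and 5 years after symptom onset reported to be 83%, 72% and 64%, respectively". The endpoint runs over the whole trial, and Protocol 3.2 expects treatment "with an average nintedanib exposure of approximately 12 months, and >2-year exposure in early enrolled patients". What is at stake is a descriptive secondary efficacy endpoint, among the data that Protocol 1.3 says will support the benefit-risk evaluation.

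**Working it through.** The documents give no hospitalisation rate, event count or precision for this endpoint, so there is no figure of the plan's own to reproduce.

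**Inputs**
- Two-year survival 0.83 (Protocol 1.3.1), measured from symptom onset in an outside cohort. Constant hazard d = −ln(0.83)/2 = 0.0932 per year. The four- and five-year figures give −ln(0.72)/4 = 0.082 and −ln(0.64)/5 = 0.089, so the level is consistent.
- Hospitalisation hazard h: not in the documents. Assumed range 0.2 to 1.0 per year.
- Times: 24/52 year, 1 year and 2 years.
- All deaths in the calculation occur without a prior respiratory hospitalisation at hazard d.

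**Formulas**
- 1 minus Kaplan-Meier: 1 − exp(−ht)
- Cumulative incidence with death competing: h/(h+d) × [1 − exp(−(h+d)t)]

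**Worked case**, h = 0.5, t = 1: 1 − exp(−0.5) = 39.3%; 0.5/0.5932 × [1 − exp(−0.5932)] = 37.7%. Gap 1.6 points.

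**Overstatement in percentage points**

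| h per year | Week 24 | Week 52 | 2 years |
|---|---|---|---|
| 0.2 | 0.2 | 0.8 | 2.7 |
| 0.5 | 0.4 | 1.6 | 4.7 |
| 1.0 | 0.7 | 2.4 | 5.3 |

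With d halved to 0.0466, the ranges are 0.1 to 0.4 at week 24, 0.4 to 1.2 at week 52 and 1.4 to 2.7 at two years.

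**Direction.** The gap has derivative h × S_h(t) × [1 − S_d(t)], where S_h and S_d are the event-free functions for hospitalisation and death. This is never negative, so the gap starts at zero and cannot shrink. In 32,000 simulated trials of 30 children, 1 minus Kaplan-Meier was never below the Aalen-Johansen estimate at weeks 24, 52 or 100. Censoring up to 4 weeks before death changed the mean gap by about 0.15 points or less.

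**Quartiles.** A curve that is too high crosses 25%, 50% and 75% too soon. With h = 0.5, Kaplan-Meier reaches 50% at ln(2)/0.5 = 1.39 years; the cumulative incidence reaches it at −ln(1 − 0.5 × 0.5932/0.5)/0.5932 = 1.52 years.

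**Small-sample illustration.** Among 10 children, one early death followed by three hospitalisations gives 1 − (8/9)(7/8)(6/7) = 33.3%, although 3 of 10 were hospitalised. With d = 0.0932, the chance of no death among 10 children by week 24 is exp(−0.0932 × 24/52 × 10) = 65%, so this is an example and not an expectation.

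**Scale.** Expected deaths among 30 children at 0.83 two-year survival, 30 × (1 − 0.83^(t/2)), are 1.3 by week 24, 2.7 by week 52 and 5.1 by two years, before removing those already hospitalised. The standard error of a 26% rate, √(0.26 × 0.74/n), is about 8 points for n = 30, 10 for n = 20 and 14 for n = 10.

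**The case against.** The strongest reply is that this is an openly stated, protocol-specified descriptive display. Kaplan-Meier with censoring at death is common, it describes the event-specific process, no test is attached, and mortality is reported in its own right. All of this is true. It supports keeping the Kaplan-Meier curve, but not reading it as the proportion of children hospitalised. The alternative reading, a rate in a setting without death, requires death to be unrelated to hospitalisation risk. That is doubtful when Protocol 1.3.1 reports that severity of illness is associated with survival.

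The death hazard used here is also probably generous. The cited survival counts from symptom onset, whereas trial patients enter later; Protocol 3.3.2 and 3.3.3 exclude FVC below 25% predicted and significant pulmonary arterial hypertension; and many deaths may follow a respiratory hospitalisation. These points stand, and are why the figure is treated as a near upper bound. Selection for clinically significant disease pulls the other way, so it is not a strict bound.

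A reader might infer that the reported rates will certainly be too high, that the quartiles will also be too high, or that the comparison of arms is materially distorted. The documents support none of these. The bias is zero without a death preceding later hospitalisations. Quartile times would be too early, not too high. The gaps at the two reported time points are small beside the sampling error. After week 24 all continuing children receive nintedanib, so the larger late gaps no longer concern a comparison with placebo. Nor does counting death as an event in the next endpoint show that this one is wrong, since that composite answers a different question.

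Finally, text around SAP 7.5.2.2 and the list of additions in SAP 4.1 are not visible, so a further analysis cannot be excluded.

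**Conclusion.** The point holds as a minor, conditional improvement. If at least one child dies without a prior respiratory hospitalisation and others are hospitalised afterwards, the planned rate overstates the actual probability of hospitalisation and the quartile times come too early; otherwise there is no bias.

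At the reported weeks the size is at most about 0.7 points (week 24) and 2.4 points (week 52). Gaps of about 3 to 5 points arise only on the late part of the curve and at the higher death hazard. These figures rest on constant hazards, an outside survival figure and an assumed hospitalisation rate. With "At least 30 randomised patients including at least 20 adolescents aged 12-17 years", the gaps at weeks 24 and 52 lie within sampling error. They are worth removing because they always point the same way and the correction uses data already collected.

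**What to change.** In SAP 7.5.2.2, for this endpoint:
- Add the Aalen-Johansen cumulative incidence at weeks 24 and 52 and for the plot, with death before respiratory hospitalisation as a competing event timed at the date of death. In that analysis, censor only children who are alive or of unknown status.
- Use it for any statement about the proportion hospitalised.
- Report, by arm, the number of deaths without prior respiratory hospitalisation.
- Keep the Kaplan-Meier display alongside, as the protocol specifies it, and declare the addition in SAP 4.1.

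The cost is a small amount of extra analysis and, if such deaths occur, a slightly lower reported rate. Death dates are already derived for SAP 5.2.2.13, with imputation rules in SAP 6.6.2.2. No data collection, test or sample size changes.

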5.2.2.13 Time to death over the whole trial

Date of death for an individual patient will be obtained from either the AE reporting page for patients with AEs leading to death or the information from the vital status assessment eCRF page. The start date of time at risk is the date of first drug intake, and, in general, patients who did not die during the trial will be censored at the last known date when the patient was alive.

[figure not shown]
For patients with known date of death (regardless of the cause of death) at any point within the trial, the time to death will be computed as:

[figure not shown]
- Date of death – date of first drug intake + 1

Patients who did not experience any event during their trial participation will be censored according to the mechanism for censoring as described in [Table 5.2.2.13: 1](#).

Table 5.2.2.13: 1 Censoring Rules for Time to death over the whole trial

[figure not shown]
Rule #	Situation	Outcome (event or censored)	Date of event or censoring
1	Patient died and date of Death is known	Event	Date of event
2	Patient died and date of Death is unknown	Event	Imputed date of event (imputation see Section 6.6.2.2)
3	Patient is alive	Censored	Date of last contact when the patient was known to be alive
4	Patient status is unknown	Censored	Date of last contact when the patient was known to be alive

[figure not shown]

5.4.1.1 Demographic data

- Gender (Male; Female)
- Ethnicity (Hispanic/Latino; Not Hispanic/Latino)
- Race: single race respondents, multiple race respondents (all combinations ticked), and all race categories regardless of how many race categories were ticked
- Age [years] at time of informed consent (transferred by IRT)*
- Age at time of informed consent (transferred by IRT) in categories [years] (≥ 6 and < 12 ; ≥ 12 and < 18)*
- Weight [kg] at baseline and historical weight (up to 2 years prior to screening) as continuous variable and in classes (< 13.5 ; ≥ 13.5 and < 23 ; ≥ 23 and < 33.5 ; ≥ 33.5 and < 57.5 ; ≥ 57.5)
- Height [cm] (standing and sitting) at baseline and historical (up to 2 years prior to screening)
- Tobacco consumption (Never, Current, Former)
- Pack years (for patients who tick “Current” or “Former” in the variable “Tobacco consumption”) as continuous variable

5.4.3 Exposure

The date of first administration is recorded at visit 2 (day 1) for the blinded period and at visit 6 (week 24) for the open-label period of the trial. The blinded exposure period ends with the first documented intake of the open-label treatment (day of visit excluded). Vice versa, the open-label exposure period begins with the first documented intake of the open-label treatment (day of visit included).

If the open-label exposure period is not started, then the double-blind exposure period ends with the day of last intake of blinded treatment.

All of the following definitions regarding exposure will be calculated separately for the double-blind period, the nintedanib exposure period and over the whole trial.

Duration of exposure [weeks] will be calculated as

$$\frac{\text{Date of last administration} - \text{date of first administration during respective period} + 1[\text{days}]}{7}$$

Treatment interruptions between date of first administration and date of last administration during the respective period will not be subtracted from this duration of exposure.

Duration of exposure will be summarized as continuous variable [weeks] and in categories:

- Double-blind period:
 - ≤2 weeks (14 days)
 - >2 to ≤6 weeks (42 days)
 - >6 to ≤12 weeks (84 days)
 - >12 to ≤18 weeks (126 days)
 - >18 to ≤24 weeks (168 days)
 - >24 weeks (168 days)

- Nintedanib exposure period:
 - ≤2 weeks (14 days)
 - >2 to ≤6 weeks (42 days)
 - >6 to ≤12 weeks (84 days)
 - >12 to ≤24 weeks (168 days)
 - >24 to ≤36 weeks (252 days)
 - >36 to ≤52 weeks (364 days)
 - >52 to ≤64 weeks (448 days)
 - >64 to ≤76 weeks (532 days)
 - >76 weeks (532 days)

Further categories might be defined if needed.

Duration of exposure on dose assigned according to weight range [weeks] will be calculated per period as

$$\frac{\text{Sum of durations on-treatment with dose effectively taken according to weight range [days]}}{7}$$

Duration of exposure on reduced dose due to AE [weeks] will be calculated per period as

Sum of durations on-treatment with reduced dose effectively taken due to AE [days]

7

Calculating the duration of exposure on dose assigned according to weight range and on reduced dose due to AE, time periods with treatment interruptions as well as on dose reduced due to other reasons will be excluded.

In case the weight of the patient on reduced dose reduces in a way to match this lower dose level, the duration of exposure on reduced dose ends.

Summary of dose changes will be presented, containing

- N (%) of patients with at least one dose reduction
- Number of dose reductions
- Reasons for dose reductions
- N (%) of patients with at least one dose increase
- Number of dose increases
- Reasons for dose increases

Off-treatment duration [weeks] will be calculated per period as

Sum of all treatment interruption durations between date of first administration and date of last administration during the respective period [days]

7

Total dose [g] will be calculated as

*Sum of durations of exposure on x g in respective period [days] *2 * x g,*

with x in 0.025, 0.05, 0.075, 0.1, 0.15.

Dose intensity [%] will be calculated as the amount of drug received during respective period multiplied by 100% and divided by the amount of drug that would have been administered, i.e. dose xx mg bid (depending on the body weight) over the respective period (or until study discontinuation).

Dose intensity [%] will be summarized as continuous variable and in categories:

- ≤30%
- >30 to ≤50%
- >50 to ≤90%
- >90 to <100%
- ≥ 100%

Exposure-related time-to-event analyses will be performed for the following items:

- Time to first dose reduction (not due to weight-based adjustment) [days]

- Time to first treatment interruption [days]
- Time to premature treatment discontinuation [days]

Time-to-event [days] for exposure-related analyses is derived based on first study drug intake in the respective study period as

$$\text{Date of event/censoring} - \text{Date of first treatment intake} + 1 \text{ day}$$

For the above mentioned time-to-event analyses patients with no such event occurred during the respective period will be censored according to the mechanism for censoring as described in [Table 5.4.3: 1](#).

Table 5.4.3: 1 Censoring rules for exposure-related time-to-event analyses

Rule #	Situation	Outcome (event/censored)	Date of event/censoring
1	Patient had a documented event during the respective period and the date of the event is known	Event	Earliest date of event
2	Patient had a documented event during the respective period and the date of the event is unknown	Event	Imputed date of event (as defined in Section 6.6.3.3)
3	Patient had no documented event during the respective period and already terminated study drug (last intake on End of treatment eCRF page available)	Censored	Date of last study drug intake
4	Patient neither had a documented event nor terminated study drug during respective period	Censored	Date of last study drug intake or end date of respective period, whichever is earlier

